[Part 2 of 2 of the document. The other parts are not shown.]

In regard to transmissibility, it is currently unknown how efficiently Omicron can spread from person to person. The replacement of Delta by Omicron as the predominant variant in South Africa raises concerns that it may be more transmissible than Delta, but because of the low number of cases in South Africa when it emerged, it is unclear if this variant is more transmissible than the Delta variant. Analysis of the changes in the spike protein indicate that Omicron is likely to have increased transmission compared to the original SARS-CoV-2 virus, but it is difficult to infer if it is more transmissible than Delta. In addition, it is unclear if infection with Omicron is associated with more severe disease. Lastly, to date there are no published data available to assess the ability of sera from vaccinated persons or those with previous SARS-CoV-2 infection to neutralize the Omicron variant.²³ Laboratory and epidemiological studies are needed to assess the impact of the Omicron variant on vaccine effectiveness and breakthrough infections, including in individuals who have received booster doses.²³

Pfizer has developed a new vaccine, BNT162b2 OMICRON (B.1.1.529), which is a BNT162b2 RNA-LNP vaccine utilizing modified RNA and encoding the P2 S containing Omicron B.1.1.529 variant-specific mutations. This new vaccine will be utilized in Substudy D. Substudy D has been designed to assess the safety, tolerability, and immunogenicity of BNT162b2 OMI within 3 different cohorts: 1) participants who have previously received 2 doses of BNT162b2 and will receive either 1 dose of BNT162b2 or 1 or 2 doses of BNT162b2 OMI; 2) participants who have previously received 3 doses of BNT162b2 and will receive a fourth dose of either BNT162b2 or BNT162b2 OMI (participants will be offered a dose of BNT162b2 OMI at Visit 404 (3-month follow-up); and 3) participants who are BNT162b2-naïve and will receive 2 doses of BNT162b2 OMI, followed by a dose of BNT162b2.

As part of protocol amendment 11, active participants in Cohort 1 and Cohort 2 at the time of this amendment will only be followed for 6 months after their last study vaccination, which aligns with the protocol-specified safety reporting period. As of Fall 2022, the recommended booster vaccine will switch to a bivalent original/Omicron-modified vaccine, and therefore it is unnecessary to prolong the participation of individuals in the study and take immunogenicity samples 12 months after vaccination for the monovalent Omicron vaccine. Their final visit will be V405.

For participants who have already completed V405 at the time of protocol amendment 11, they will be informed by the investigator site staff of study completion and that no further visits are required.

As part of protocol amendment 12, endpoints and/or analyses that do not pertain to current variant-modified versions of BNT162b2 were removed to expedite remaining testing and to focus on analyses of interest.

See Section 2.2 for the study background.

10.10.2.2. Benefit/Risk Assessment

No additional risks are identified for Substudy D beyond those detailed for the master study (see Section 2.3).

10.10.2.2.1. Benefit Assessment

Benefits to individual participants enrolled in Substudy D may be:

- Receipt of a third, fourth, or fifth dose of an efficacious or potentially efficacious COVID-19 vaccine that may convey a longer duration of protection during a global pandemic.
- Contributing to research to help others in a time of global pandemic.

10.10.3. Objectives, Estimands, and Endpoints

| Objectives | Estimands | Endpoints |
|---|---|--|
| | Primary Safety | |
| To describe the safety and tolerability profile of BNT162b2 OMI given as the third, fourth, or fifth dose to BNT162b2-experienced participants, or as a 2-dose series to COVID-19 vaccine—naïve participants To describe the safety and tolerability profile of BNT162b2 given as a third or fourth dose to BNT162b2-experienced participants (Group 2b, Group 4, and Group 5) | In participants receiving at least 1 dose of study intervention, the percentage of participants reporting: Local reactions for up to 7 days following each dose Systemic events for up to 7 days following each dose AEs from the first study vaccination (received in this study) through 1 month after the last study vaccination SAEs from the first study vaccination (received in this study) through 6 months after the last study vaccination | Local reactions (pain at the injection site, redness, and swelling) Systemic events (fever, fatigue, headache, chills, vomiting, diarrhea, new or worsened muscle pain, and new or worsened joint pain) AEs SAEs |
| | Primary Immunogenicity BNT162b2-experienced participants | |
| G1vG2bA: To descriptively compare the anti-Omicron immune response after 1 dose of BNT162b2 OMI to after 1 dose of BNT162b2 given as the third dose in BNT162b2-experienced participants | In participants complying with the key protocol criteria (evaluable participants) and with evidence of past SARS-CoV-2 infection: • GMR of the Omicron-neutralizing titers at 1 month after 1 dose of BNT162b2 OMI to those at 1 month after 1 dose of BNT162b2 given as the third dose in BNT162b2-experienced participants • The difference in percentages of participants with seroresponse to the Omicron strain at 1 month after 1 dose of BNT162b2 OMI and at 1 month after 1 dose of BNT162b2 given as the third dose in BNT162b2-experienced participants | SARS-CoV-2 Omicron-neutralizing titers |
| G2vG2bA: To descriptively compare the anti-Omicron immune response after 2 doses of BNT162b2 OMI given as the third and fourth dosesto after 1 dose of BNT162b2 given as the third dose in BNT162b2-experienced participants | In participants complying with the key protocol criteria (evaluable participants) and with evidence of past SARS-CoV-2 infection: • GMR of the Omicron-neutralizing titers at 1 month after 2 doses of BNT162b2 OMI to those at 1 month after 1 dose of BNT162b2 given as the third (and fourth) dose in BNT162b2-experienced participants • The difference in percentages of participants with seroresponse to the Omicron strain at 1 month after 2 doses of BNT162b2 OMI and at 1 month after 1 dose of BNT162b2 given as the third (and fourth) dose in BNT162b2-experienced participants | SARS-CoV-2 Omicron-neutralizing titers |

| Objectives | Estimands | Endpoints |
|---|--|---|
| G3vG4A: To demonstrate the superiority with respect to level of neutralizing titer and noninferiority with respect to seroresponse rate of the anti-Omicron immune response after 1 dose of BNT162b2 OMI compared to after 1 dose of BNT162b2 given as the fourth dose in BNT162b2-experienced participants | In participants complying with the key protocol criteria (evaluable participants) and no serological or virological evidence (up to 1 month after receipt of 1 dose of study intervention) of past SARS-CoV-2 infection: • GMR of the Omicron-neutralizing titers at 1 month after 1 dose of BNT162b2 OMI to those at 1 month after 1 dose of BNT162b2 given as the fourth dose in BNT162b2-experienced participants • The difference in percentages of participants with seroresponse to the Omicron strain at 1 month after 1 dose of BNT162b2 OMI and at 1 month after 1 dose of BNT162b2 given as the fourth dose in BNT162b2-experienced participants | SARS-CoV-2 Omicron-neutralizing titers |
| | COVID-19 vaccine–naïve participants | |
| G5A: To demonstrate the superiority with respect to level of neutralizing titer and noninferiority with respect to seroresponse rate of the anti-Omicron immune response after 2 doses of BNT162b2 OMI compared to after 2 doses of BNT162b2 in participants ^b selected from the C4591001 study | In participants complying with the key protocol criteria (evaluable participants) and with or without serological or virological evidence (up to 1 month after receipt of the second dose of BNT162b2 OMI or BNT162b2 as appropriate) of past SARS-CoV-2 infection: • GMR of the Omicron-neutralizing titers 1 month after the second dose of BNT162b2 OMI to 1 month after the second dose of BNT162b2 in participants selected from the C4591001 study • The difference in percentages of participants with seroresponsea to the Omicron strain at 1 month after the second dose of BNT162b2 OMI and at 1 month after the second dose of BNT162b2 in participants selected from the C4591001 study | SARS-CoV-2 Omicron-neutralizing titers |
| | Secondary Immunogenicity BNT162b2-experienced participants | |
| G3vG4B: To demonstrate the "super" superiority of the anti-Omicron immune response after 1 dose of BNT162b2 OMI compared to after 1 dose of BNT162b2 given as the fourth dose in BNT162b2-experienced participants | Same as GMR estimand of G3vG4A | Same as G3vG4A |

| Objectives | Estimands | Endpoints |
|---|---|--|
| | COVID-19 vaccine-naïve participants | |
| G5B: To demonstrate the "super" superiority of the anti-Omicron immune response after 2 doses of BNT162b2 OMI compared to after 2 doses of BNT162b2 in participants ^b selected from the C4591001 study | Same as GMR estimand of G5A | Same as G5A |
| | Exploratory | |
| To describe the immune response to BNT162b2 OMI or BNT162b2 given as the third and/or fourth and/or fifth dose in BNT162b2-experienced participants | For Cohort 1: at baseline, 1 month after the first study vaccination, and 1 month after the second study vaccination (Group 2 only), For Cohort 2: at baseline, 1 month and 3 months after the first study vaccination, and 1 month, 3 months, and 6 months after the last study vaccination: | SARS-CoV-2 Omicron-neutralizing titers SARS-CoV-2 reference-strain-neutralizing titers |
| | GMT at each time point GMFRs from before the first dose of study intervention to subsequent time points Percentages of participants with seroresponse^a at each time point | |
| To describe the immune response to BNT162b2 OMI in COVID-19 vaccine—naïve participants | At baseline, 1 month and 6 months after Dose 2, and 1 month and 6 months after Dose 3: GMT at each time point GMFRs from before the first dose of BNT162b2 OMI to subsequent time points Percentages of participants with seroresponse at each time point | SARS-CoV-2 Omicron-neutralizing titers SARS-CoV-2 reference-strain–neutralizing titers |
| To describe the immune response to the reference strain and VOCs in a subset of 30 participants ^c per group | | SARS-CoV-2 neutralizing titers for the reference strain and VOCs |
| To describe the immune response to any VOCs not already specified (eg, Delta) | | SARS-CoV-2 neutralizing titers for any VOCs not already specified (eg, Delta) |
| To describe confirmed COVID-19 and severe COVID-19 cases | | Confirmed COVID-19 cases Confirmed severe COVID-19 cases Strain sequencing of COVID-19 cases |

| Objectives | Estimands | Endpoints |
|---|-----------|-----------|
| To describe the cell-mediated immune response, and additional humoral immune response parameters, to the reference strain and Omicron in a subset of participants with PBMC samples collected in each group | | |

- a. Seroresponse is defined as achieving a ≥4-fold rise from baseline (before the first dose of study vaccination). If the baseline measurement is below the LLOQ, the postvaccination measure of ≥4 × LLOQ is considered seroresponse.
- b. A subset of approximately 175 participants (18 through 55 years of age) from Study C4591001 who have received 2 doses of BNT162b2 30 μg will be selected for this objective. The subset selected from Study C4591001 will include a similar percentage of participants with a positive SARS-CoV-2 infection status at baseline as Group 5 of this substudy, whenever feasible.
- c. This subset of participants will not contribute to the assessment of primary and secondary immunogenicity objectives.

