10.10.4. Study Design

10.10.4.1. Overall Design

This is a randomized substudy composed of open-labeled and observer-blinded groups to evaluate the safety, tolerability, and immunogenicity of a 2-dose primary series of BNT162b2 OMI, and as a booster (third, fourth, or fifth) dose at investigator sites in the US and South Africa only. Participants ≥18 years of age to ≤55 years of age will be enrolled. Approximately 1420 participants will be enrolled in the study.

Participants in Cohort 1 will have completed a 2-dose primary series of BNT162b2 (30-µg doses), with their last dose 90 to 240 days prior to enrollment. Approximately 615 participants will be randomized at a ratio of 1:1:1 either to receive 1 dose (third) of BNT162b2 OMI, 2 doses (third and fourth) of BNT162b2 OMI, 4 weeks apart, or 1 dose (third) of BNT162b2. Randomization will be stratified by age (stratified as 18-30 and 31-55 years of age). Participants in Cohort 1 will remain blinded to whether they will be receiving a fourth dose through 1 month after their first dose, but the investigator and sponsor will not be blinded.

Participants in Cohort 2 will be enrolled from Study C4591001 and C4591031 Substudy A and will have completed a 2-dose primary series and received a single booster (third) dose of BNT162b2, with their last dose 90 to 180 days prior to randomization. Approximately 600 participants will be randomized at a ratio of 1:1 to receive a fourth dose of either BNT162b2 or BNT162b2 OMI at Visit 401. Participants will be offered a dose of BNT162b2 OMI at Visit 404 (3-month follow-up). Randomization will be stratified by age (stratified as 18-30 and 31-55 years of age). Cohort 2 will be observer-blinded.

In Cohort 3, 205 participants 18 through 55 years of age who are COVID-19 vaccine—naïve and have not experienced COVID-19 will be enrolled to receive 2 doses (primary series) of BNT162b2 OMI, 3 weeks apart, with a dose of BNT162b2 approximately 5 months later. If participants do not consent to receive BNT162b2 as a third dose, they will not receive a third dose. No participants should receive BNT162b2 OMI as a third dose.

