10.10.6.1.1. Administration

For Cohorts 1 and 2, participants will receive 1 dose of study intervention as allocated by the IRT at Visit 401 (third or fourth dose) in accordance with the substudy's SoA (Section 10.10.1.3). Group 2 participants will receive a second dose of BNT162b2 OMI at Visit 402. Group 3 and Group 4 participants may receive a dose of BNT162b2 OMI at Visit 404.

For Cohort 3, COVID-19 vaccine—naïve participants will receive 1 dose of BNT162b2 OMI at Visit 501 and Visit 502, and 1 dose of BNT162b2 at Visit 506. Vaccination 3 may be administered as early as 5 months (150 days) after Vaccination 2.

Study intervention should be administered intramuscularly into the deltoid muscle, preferably of the nondominant arm, by an **unblinded** administrator.

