10.10.6.2. Measures to Minimize Bias: Randomization and Blinding

10.10.6.2.1. Blinding of Site Personnel

In Cohort 1 (Groups 1 and 2b) and Cohort 2, the study staff receiving, storing, dispensing, preparing, and administering the study interventions will be unblinded. All other study and site personnel, including the investigator, investigator staff, and participants, will be blinded to study intervention assignments. In particular, the individuals who evaluate participant safety will be blinded.

The PI will assign the responsibility of the unblinded dispensers/administrators to persons who will not participate in the evaluation of any study participant. To ensure adequate coverage, at least 2 unblinded dispensers/administrators will be assigned per site. Members of the study site staff or clinic pharmacy should fulfill these roles. Contact between the unblinded dispensers and study participants should be kept to a minimum. The investigator, study coordinator, and any site staff other than the unblinded dispensers/administrators must not be allowed to know the study intervention assigned to any study participant and must not be allowed to see the study intervention container contents. In the event of a Quality Assurance audit, the auditor(s) will be allowed access to unblinded study intervention records at the site(s) to verify that randomization/dispensing has been done accurately.

The group of participants who will be enrolled to receive a third and fourth dose of BNT162b2 OMI (Group 2 of Cohort 1) will remain blinded to whether they will be receiving a fourth dose, through 1 month after their first dose of BNT162b2 OMI, but the investigator and sponsor will not be blinded.

Participants in Cohort 2 will be unblinded to confirm the vaccine received once they have completed Visit 404 (3 months after Substudy D Vaccination 1).

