 - Fever $\ge 39.0^{\circ}\text{C} (\ge 102.1^{\circ}\text{F})$.
 - Redness or swelling at the injection site measuring greater than 10 cm (>20 measuring device units).

- Severe pain at the injection site.
- Any severe systemic event.
- Ask the participant to contact the site staff or investigator if the participant experiences acute chest pain, shortness of breath, or palpitations (see Section 10.10.8.6.7).
- Ask the participant to contact the site staff or investigator if a medically attended event (eg, doctor's visit, emergency room visit) or hospitalization occurs.
- Ask the participant to contact the site staff or investigator (this could be via the COVID-19 illness e-diary) immediately if he or she experiences any respiratory symptoms as detailed in Section 10.10.8.6.4.1.
- Schedule an appointment for the participant to return for the next study visit.
- Remind the participant to bring the reactogenicity e-diary to the next visit.
- Complete the source documents.
- The investigator or an authorized designee completes the CRFs and an unblinded dispenser/administrator updates the study intervention accountability records.
- The investigator or appropriately qualified designee reviews the reactogenicity e-diary data online following vaccination to evaluate participant compliance and as part of the ongoing safety review. Daily review is optimal during the active diary period.

10.10.8.6.1.2. Visit 402 – 1-Month Follow-Up Visit (After Substudy D Vaccination 1) (28 to 35 Days After Visit 401)

- Record AEs as described in Section 8.3.
- Review the participant's reactogenicity e-diary data. Collect stop dates of any reactogenicity e-diary events ongoing on the last day that the reactogenicity e-diary was completed and record stop dates in the CRF if required.
- Record nonstudy vaccinations as described in Section 6.8.
- Record details of any of the prohibited medications specified in Section 6.8.1 received by the participant if required for his or her clinical care.
- For participants who are HIV-positive, record the latest CD4 count and HIV viral load.
- Discuss contraceptive use as described in Section 5.3.
- Collect a blood sample for immunogenicity testing.

• If the participant is part of the group for description of cell-mediated immune response (select sites only), collect a blood sample (approximately 120 mL) for PBMC isolation.

Only if the participant is to receive a second dose of BNT162b2 OMI (Substudy D Vaccination 2):

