10.10.9.3.2. Primary Endpoint(s)/Estimand(s) Analysis

| Endpoint | Statistical Analysis Methods |
|----------------|--|
| Safety | • Descriptive statistics will be provided for each reactogenicity endpoint for each vaccine group. Local reactions and systemic events from Day 1 through Day 7 after each study vaccination (where Day 1 is the day of vaccination) will be presented by severity and cumulatively across severity levels. Descriptive summary statistics will include counts and percentages of participants with the indicated endpoint and the associated Clopper-Pearson 95% CIs. |
| | AEs and SAEs will be categorized according to MedDRA terms. Counts, percentages, and associated Clopper-Pearson 95% CIs of AEs within 1 month and SAEs within 6 months after the last study vaccination will be provided for each vaccine group. |
| Immunogenicity | For each primary immunogenicity estimand described in Section 10.10.3 |
| | • GMRs and the associated 2-sided 95% CIs will be calculated using the method described in Section 9.3.1.2.3. |
| | • The percentages of participants with seroresponse for each group will be provided. The difference in percentages of participants with seroresponse and the associated 2-sided 95% CIs will be calculated using the Miettinen and Nurminen method (see Section 9.3.1.1). |
| | • For Cohort 1, only participants with evidence of past SARS-CoV-2 infection will be included in the analysis. For Cohort 2, only participants with no serological or virological evidence (up to 1 month after receipt of 1 dose of study intervention) of past SARS-CoV-2 infection will be included in the analysis. |
| | • For Cohort 2 and Cohort 3, superiority based on GMR will be established if the lower bound of the 2-sided 95% CI for the GMR is >1; noninferiority based on seroresponse rate difference will be established if the lower bound of the 2-sided 95% CI for the difference in percentage is greater than -5%. |

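### Substudy D, Cohort 1: the one-dose OMI contrast (G1vG2bA) uses Group 1 only, although Group 2 has a randomized, pre-second-dose sample that would narrow the interval by about 13% on the log scale

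*Protocol*

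**What the plan says.** Section 10.10.4.1 describes the Cohort 1 allocation: "Approximately 615 participants will be randomized at a ratio of 1:1:1 either to receive 1 dose (third) of BNT162b2 OMI". That is Group 1. The second arm, Group 2, is assigned "2 doses (third and fourth) of BNT162b2 OMI, 4 weeks apart". The third arm, Group 2b, is given BNT162b2 once. Table 10 gives 205 participants to each of Groups 1, 2 and 2b.

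Section 10.10.6.1.1 fixes the point at which Groups 1 and 2 diverge: "Group 2 participants will receive a second dose of BNT162b2 OMI at Visit 402". In the Visit 402 procedures (Section 10.10.8.6.1.2, 28 to 35 days after Visit 401), the immunogenicity draw is listed for every Cohort 1 participant. It comes ahead of a block introduced by "Only if the participant is to receive a second dose of BNT162b2 OMI (Substudy D Vaccination 2".

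Section 10.10.3 states the primary one-dose objective as "G1vG2bA: To descriptively compare the anti-Omicron immune response after 1 dose of BNT162b2 OMI to after 1 dose of BNT162b2". The estimand is worded by treatment and time, in evaluable participants with evidence of past infection, and only the label restricts it to Groups 1 and 2b. Group 2 enters the primary objectives solely through G2vG2bA, after its second dose. For Cohort 1 the exploratory objective covers baseline, "1 month after the first study vaccination, and 1 month after the second study vaccination (Group 2 only". The restriction to Group 2 attaches to the last time point, so Group 2 is not excluded from the one after dose 1.

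Section 10.10.9.5 draws a random sample of about 100 previously infected participants from each of the three groups. Section 10.10.9.1.3 says that Cohort 1 carries no hypothesis.

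**The concern.** Up to the Visit 402 draw, Groups 1 and 2 are two random samples given the same vaccine on the same schedule, and Group 2 participants do not know whether another dose will follow. Group 2's Visit 402 titers therefore meet the wording of the G1vG2bA estimand. About half of the sampled one-dose OMI results nevertheless stay outside the contrast with BNT162b2, and the protocol gives no reason.

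What is at stake is precision. Cohort 1 is Substudy D's only randomized comparison of OMI with BNT162b2 as a third dose; Cohort 2 concerns the fourth dose, and Cohort 3 takes its control from another study. Because Cohort 1 has no test, the estimate and its interval are the whole result, and the interval could be narrower without new samples.

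**Working it through.** **Inputs (Section 10.10.9.5 unless noted)**
- Log-scale SD 0.93, from the C4591001 study.
- About 100 previously infected participants sampled per Cohort 1 group.
- For Cohorts 2 and 3: 175 per group, 35% nonevaluable or previously infected, true GMR 1.5, 1-sided alpha 0.025, stated power 90.6%.
- No precision or power is stated for Cohort 1.

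**Step 1: reproduce the protocol's figure.** 175 × 0.65 = 113.75, or 114. SE of ln GMR = 0.93 × √(2/114) = 0.1232, and ln 1.5 / 0.1232 = 3.29. The normal approximation gives 90.9% and the noncentral t gives 90.6%, as stated. The SD is therefore on the natural-log scale and the formula is the expected one.

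**Step 2: the one-dose contrast as written, 100 versus 100.** SE = 0.93 × √(1/100 + 1/100) = 0.1315. The half-width is 1.96 × 0.1315 = 0.2578, so the CI is GMR ×/÷ exp(0.2578) = 1.294 (1.296 with the t quantile).

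**Step 3: Groups 1 and 2 combined versus Group 2b at Visit 402, 200 versus 100.** SE = 0.93 × √(1/200 + 1/100) = 0.1139. The half-width is 1.96 × 0.1139 = 0.2232, so the CI is GMR ×/÷ 1.250 (1.251 with the t quantile).

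**Step 4: relative gain.** √(1/200 + 1/100) / √(2/100) = 0.866, or 13.4% narrower on the log scale. This ratio holds for any SD and any common group size. It equals a balanced comparison with 2 / (1/200 + 1/100) = 133 per group. The gain is limited because Group 2b stays at about 100.

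**Step 5: sensitivity to the SD.** The protocol gives no SD for previously infected Cohort 1 participants. The rows at 0.7 and 1.2 are assumptions (t-based factors):

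| SD (ln) | Group 1 alone v 2b | Groups 1+2 v 2b |
|---|---|---|
| 0.70 | 1.216 | 1.184 |
| 0.93 | 1.296 | 1.251 |
| 1.20 | 1.397 | 1.335 |

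**Step 6: seroresponse difference.** The protocol's 80% and 60%, set for Cohorts 2 and 3, are borrowed here as an assumption. The half-width is 1.96 × √(0.16/100 + 0.24/100) = 12.4 percentage points with Group 1 alone, and 1.96 × √(0.16/200 + 0.24/100) = 11.1 points with the groups combined.

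**The case against.** The strongest reply is that nothing here is wrong. Group 1 versus Group 2b compares two randomized arms as assigned, is unbiased, and is declared descriptive. The sponsor chose to sample about 100 from about 175 per group, so the precision was a choice. That stands, and it limits the point to an efficiency improvement.

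There are also sound reasons not to make the combined group the primary:
- **Blinding.** For Group 2, participants are blinded to the fourth dose, "but the investigator and sponsor will not be blinded". Site and sponsor blinding in Cohort 1 is confined to Groups 1 and 2b, so that pair has matching blinding. The serology laboratory is blinded throughout (Section 10.10.6.2.2). This protects titers but not investigator-assessed events.
- **Evaluability.** The evaluable set in Section 10.10.9.2 requires receipt of the assigned intervention(s). For Group 2 this may mean both doses, which would condition a Visit 402 result on a later event.
- **Infection status.** Among the Cohort 1 groups, only Group 2 has a Visit 402 swab (Section 10.10.8.6.6). The Cohort 1 analysis requires evidence of past infection and states no cutoff for it, so ascertainment could differ between groups.

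Three stronger readings might be inferred, and the documents support none of them:
- *The Group 2 data are discarded.* They are not; the exploratory objective covers the time point after dose 1.
- *The report will hold two competing estimates of one effect.* For Cohort 1, Section 10.10.9.3.4 plans within-group GMTs, GMFRs and seroresponse percentages after dose 1. It specifies no Group 2 versus 2b contrast at Visit 402.
- *Dose-1 safety loses half its chance of showing an uncommon event.* At a true rate of 0.5%, the chance of at least one event is 1 − 0.995^205 = 0.64 in 205 participants and 1 − 0.995^410 = 0.87 in 410, which is not half. More to the point, "Descriptive statistics will be provided for each reactogenicity endpoint for each vaccine group" after each vaccination, so dose-1 reactions in all 410 are already tabulated. A combined adverse-event comparison would also mix unblinded with blinded assessment.

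**Conclusion.** The point holds as a cheap improvement. The one-dose contrast is valid as written, but its interval is wider than the collected data allow: about ×/÷ 1.29 against ×/÷ 1.25 at SD 0.93 and 100 per group, or 13% on the log scale. The relative gain does not depend on the SD; the absolute factors do.

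The size rests on three assumptions: similar evaluable numbers in the three groups, a common SD, and Visit 402 assays for the roughly 100 participants sampled from Group 2. The last is implied by the exploratory objective but not spelled out for that sample. No conclusion, error rate or safety finding is at risk.

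**What to change.** Keep Group 1 versus Group 2b as the descriptive primary and leave G2vG2bA as it is. Prespecify, before group results are known, a supplementary GMR and seroresponse difference at Visit 402 for Groups 1 and 2 combined versus Group 2b, with two conditions:

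1. Use a dose-1 evaluable set: correct Visit 401 vaccine, valid Visit 402 result within the window, and no important deviation up to that draw. Receipt of Group 2's second dose is not required.
2. Define evidence of past infection identically in Groups 1, 2 and 2b, leaving out the Visit 402 swab that only Group 2 has. Because the samples of about 100 are drawn from participants with such evidence, the definition should govern the sampling as well.

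The cost is one extra analysis and one extra evaluability definition. No visit, blood sample or alpha is added, and no assay either if the Group 2 sample is tested at Visit 402 as the exploratory objective implies.
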